- *Laser Doppler Flowmeter (LDF):* Measurements obtained from LDF pulse oximeter gives a series of reading of blood velocity. LDF measurements would be used for teeth that are planned for extraction and also up to 2-5 additional teeth in each participant

STUDY DESIGN

Standard Care Procedures:

Participants may receive the following treatment procedures whether he/she join this study or not:

- Review of medical and dental history
- Oral examinations
- Dental Procedures (e.g., extractions) planned by his/her oral surgery provider

Study-Related Procedure

- The researcher will gather information initially by asking if any of the teeth are hurting or sensitive to hot/cold
- Participants will complete self-report questionaries' regarding their history of dental pain
- Existing panoramic radiograph will be reviewed by a member of research team prior to choosing which teeth (less than 10) will be to be tested.
- Blood pressure, and heart rate values would be recorded on this appointment from your medical record by a member of research team prior to the extraction.
- The researcher initially will palpate the gum around selected teeth and record any discomfort
- A plastic clip, pulse oximeter will be placed over the teeth, one at a time, to measure blood flow by measuring the presence of pulse in these teeth for approximately for 15-30 seconds.
- The clip will remain on the tooth for additional 2-3 minutes to continually measuring pulse while the following tests are taken place:
 - **Cold Testing**: This test is used to assess if the tooth is "dead" or "alive" by measuring sensation of cold from the tooth. A small cotton ball will be sprayed with cold spray (called Endo-Ice) and then placed on the surface of that tooth for approximately 15 seconds or till participant reports any sensation of cold. There would be 30 seconds wait time prior to the next step.
 - **Electrical Pulp Testing:** This test is used to assess if the tooth is "dead" or "alive" by measuring sensation of electrical pulses from the tooth. A small probe attached to an electrical pulp testing (EPT) device will be placed on the surface of that tooth for approximately 15 seconds or till participant reports any tingling sensation. There would be 30 seconds wait time prior to the next step.

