 - **Percussion Testing:** This test is used to assess if the tooth is "dead" or "alive". The end of the mouth mirror is used to gently tap on the tooth surface and record any discomfort. There would be 30 seconds wait time prior to removal of the clip.
 - 0
- Once the tests above are completed, the plastic clip will be removed from your tooth. The pulse oximeter sensors will be removed from the plastic clip and replace with the LDF sensor. The plastic clip will be placed back over the teeth previously tested to measure the blood flow with the LDF. Blood flow will be measured by the presence of a pulse in each tooth for approximately for 15-30 seconds. Once the measurement is obtained, the plastic clip will be removed from the tooth.

- After obtaining participant's permission, researchers will obtain a de-identified copy of the participants dental radiographs
- After planned extraction is completed by the oral surgery provider, the tooth/teeth from the standard of care procedure will be provided to the researcher for further analysis to determine of the tooth is "alive or dead". This process will occur at the University of Michigan School of Dentistry Oral Surgery Clinics.
- Upon completion of extraction, the teeth will be placed in formalin-containing bottle. After formalin fixation, the teeth will be prepared for histological examination using 10% EDTA for demineralization. Following that, the teeth are trimmed, embedded in paraplast and cut longitudinally to obtain 6um thick section. The sections were stained with H&E and examined with a light microscope. The histological diagnosis are based on the classification used by Seltzer et al. as follow:
 - 1. Normal Pulp: Intact, uninflamed pulp
 - 2. Transitional Stage: Intact pulp with scattered inflammatory cells
 - 3. Pulpitis: inflammatory process affecting the coronal and radicular
 - 4. Pulp Necrosis: All pulp tissue is necrotic

STUDY ENROLLMENT AND WITHDRAWAL

1.6 **Subject Inclusion Criteria**

In order to be eligible to participate in this study, you must meet the following criteria:

- 1. Must be a patient of the University of Michigan School of Dentistry Oral Surgery Clinics
- 2. Must be scheduled for at least one tooth extraction at Oral Surgery Clinic
- 3. Must be 18 to 65 years old
- 4. Must be able to understand and willing to cooperate with all study procedures
- 5. Must be able to sign an IRB-approved written consent

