- 6. Must have at least two teeth with an intact crown, without any full metallic crown coverage, and/or previous root canal treatments
- 7. Must have no history of spontaneous pain, and/or lingering pain to cold/hot in teeth that are not going to be extracted on that day.
- 8. If one of the teeth mentioned in inclusion #6 is being extracted, be willing to give your extracted tooth/teeth for further analysis to determine of the tooth is "alive or dead"

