1.20 Study Hypotheses

The calculations are based on a comparison of the test results and "true" disease status. The sensitivity, specificity, and positive and negative predictive values of heat and cold application and electrical pulp tests will be calculated. Teeth are grouped into two categories, healthy, true disease (irreversible pulpitis and necrosis). A perfect diagnostic test would always be positive in the presence of disease and negative in the absence of disease. Therefore, sensitivity, specificity, and positive and negative predictive value have been developed to characterize test accuracy and to compute the benefits of test usage. In addition to that, clinical measurements of the extracted teeth will be compared with identification of the true disease by histological evaluation for the pulp status.

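### Cold and EPT are described only as dead/alive tests, but section 1.20 scores them against a disease group that includes irreversible pulpitis and never defines a positive result

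*Combined protocol and SAP*

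**What the plan says.** The Protocol Summary and the Study Design (Study-Related Procedure) give cold testing one purpose: "This test is used to assess if the tooth is 'dead' or 'alive' by measuring sensation of cold from the tooth". The cotton ball is "placed on the surface of that tooth for approximately 15 seconds or till participant reports any sensation of cold". EPT has the same purpose, and its probe is "placed on the surface of that tooth for approximately 15 seconds or till participant reports any tingling sensation". Neither description asks for intensity, duration after removal, or an EPT cut-off. A 30-second wait follows each test.

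Section 1.20 then states: "The sensitivity, specificity, and positive and negative predictive values of heat and cold application and electrical pulp tests will be calculated". The target is set as follows: "Teeth are grouped into two categories, healthy, true disease (irreversible pulpitis and necrosis". On the meaning of positive it says only: "A perfect diagnostic test would always be positive in the presence of disease and negative in the absence of disease". It does not say which cold or EPT result is positive.

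The histology scheme (Study Design and section 1.15) lists pulpitis separately from necrosis: "Pulpitis: inflammatory process affecting the coronal and radicular". Only the necrosis class is described as wholly dead tissue.

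Inclusion criterion 7 in section 1.6 reads: "Must have no history of spontaneous pain, and/or lingering pain to cold/hot in teeth that are not going to be extracted on that day".

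**The concern.** A present/absent reading suits the alive/dead question. It does not suit a disease group that combines dead pulps with inflamed pulps that are not wholly dead. If no response is positive, inflamed teeth that respond are missed. If a response is positive, healthy teeth that respond are called diseased. No single present/absent coding is right for both parts of the section 1.20 disease group.

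Criterion 7 shows that the protocol treats lingering pain to cold or heat as a reason to keep a tooth out of the non-extraction set. Teeth with such a history are therefore left among those being extracted, and these are the teeth that go to histology. Yet nothing tells the examiner to record lingering when cold is applied. If it is not recorded at the chair, it cannot be recovered in the analysis.

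At stake are the accuracy figures planned in section 1.20. Low sensitivity and negative predictive value (NPV) could reflect the scoring and not the tests. With no written rule, the coding could also differ between examiners or be chosen after the data are seen.

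**Working it through.** The plan has no accuracy figure to reproduce. Its only numerical design figure is the 35 completers in section 1.21, which has no stated inputs and does not bear on this point.

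**Inputs.** From the documents: the dead/alive endpoint (Study Design) and the disease group of irreversible pulpitis plus necrosis (section 1.20). Assumed, because the documents do not give them:
- f, the share of diseased teeth that have irreversible pulpitis: 0.25 to 0.75
- r, the probability that such a tooth gives any response: 0.7 to 1
- Se_nec, the probability that a necrotic tooth gives no response: 1 (best case), with 0.9 as a check
- disease prevalence 0.5 and specificity 0.9, for NPV only

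**Sensitivity when no response is positive.**

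Se = (1 − f)·Se_nec + f·(1 − r)

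With Se_nec = 1 this becomes 1 − f·r, the highest value the rule can reach:

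| | f = 0.25 | f = 0.50 | f = 0.75 |
|---|---|---|---|
| r = 1.0 | 0.75 | 0.50 | 0.25 |
| r = 0.9 | 0.775 | 0.55 | 0.325 |
| r = 0.7 | 0.825 | 0.65 | 0.475 |

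At f = 0 the ceiling is 1.00, so the limit comes entirely from including pulpitis in the target. With Se_nec = 0.9 and f = 0.5, sensitivity is 0.45 at r = 1 and 0.60 at r = 0.7.

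**NPV.**

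NPV = Sp(1 − p) / [Sp(1 − p) + (1 − Se)p], with p = 0.5 and Sp = 0.9

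- f = 0: 1.00
- f = 0.25, r = 1: 0.45 / (0.45 + 0.125) = 0.783
- f = 0.50, r = 1: 0.45 / (0.45 + 0.25) = 0.643
- f = 0.75, r = 1: 0.45 / (0.45 + 0.375) = 0.545
- f = 0.50, r = 0.7: 0.45 / (0.45 + 0.175) = 0.72

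**Reversed coding.** If any response is positive, sensitivity with Se_nec = 1 is f·r, which is 0.50 at f = 0.5, r = 1. Specificity becomes 1 − 0.9 = 0.10 under the same assumption. Reversing the code does not solve the problem.

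**The case against.** The strongest reply is that the plan writes down no scoring rule, so it cannot be said to contain a wrong one. Section 1.20 does not define a positive result. Form 2 has an open reading cell for each test, not a yes/no box. Section 1.5 speaks of a conventional pulpal diagnosis that also uses percussion and palpation, and section 1.22 plans correlations and t-tests, which suggests that not every reading was meant to be binary. This stands. A reader might infer that responding pulpitis teeth are negative by construction, but the documents support only the conditional: if any sensation is scored as negative. The open cell and the wider diagnosis do not close the gap, because no section grades a response, combines the tests or sets a cut-off.

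Stopping the stimulus at the first sensation also does not prevent lingering from being seen, since lingering appears after removal. That stands too: the gap is in recording and scoring, not in how the stimulus is applied.

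The documents do not say that irreversibly inflamed pulps always respond, or respond with lingering pain. They support only that such pulps are not wholly necrotic. This is why r is an assumption and is varied.

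A reader might further infer that the oximeter would look better than cold and EPT for this reason alone. The documents do not support that. Section 1.20 does not list the oximeter among the tests whose accuracy is calculated. Section 1.22 makes cold and EPT the oximeter's gold standard, so disagreement there counts against the oximeter. The Study Design has the oximeter measure presence of a pulse, which an inflamed but living pulp may also show.

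Finally, the opening symptom question and the cold item in the dental pain questionnaire collect symptoms, but neither is tied to a test result on a given tooth.

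**Conclusion.** The mismatch is real and should be corrected. A dead/alive endpoint is to be scored against a disease group that includes pulps that are not dead, and no rule connects the two. On the only reading the plan states, sensitivity cannot exceed 1 − f·r. The direction holds for any f and r above zero. The size depends wholly on those two assumed quantities, from 0.825 (f = 0.25, r = 0.7) down to 0.25 (f = 0.75, r = 1) over the range shown.

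The reach is limited to the accuracy statistics of section 1.20. The primary outcome in section 1.5 is a correlation between subjective and objective measurements, histology is exploratory, and presence of sensation is a coherent endpoint for the alive/dead aim.

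**What to change.** 1. In section 1.20, state in advance what counts as positive for each test, and report accuracy against two targets: (a) necrosis versus not necrosis, with no response as positive for both cold and EPT; (b) pulpitis or necrosis versus healthy. For (b), also state how the histology classes map to the groups, since section 1.20 says irreversible pulpitis, the histology list says only pulpitis, and the transitional stage is unassigned.
2. On Form 2, record the cold response as none, normal, exaggerated or lingering, with seconds until it resolves or a note that it is still present at 30 seconds. Observe this in the wait that already follows the cold test. Record a test stopped as intolerable as a response, not as missing. For target (b), count cold as positive if there is no response or an exaggerated or lingering one, and show the result beside the no-response rule.
3. Report EPT for target (b) only with a statement that a response/no-response reading cannot separate responding pulpitis from healthy pulp.

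The cost is one more self-reported field on Form 2 and a few sentences in the protocol. No stimulus or visit time is added. Timing is capped at 30 seconds. The combined cold rule can only add positives, so it may lower specificity; this is why both rules should be shown.

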Previous studies have shown the potential application of conventional pulse oximeter for assessment of the presence of dental pulp vascularity using a modified probe for teeth. (Alghaithy and Qualtrough 2017) It also appears that there is a correlation between oxygen saturation of pulpal circulation with systemic blood using pulse oximeter.(Schnettler and Wallace 1991)

Objective diagnostic devices such as pulse oximeter could be valuable not only in pulp necrosis but also in diagnosis of inflammatory status of the pulp. If blood flow in teeth is related to symptoms and/or pathology, this would likely have much broader applicability in dentistry, as dentists frequently struggle to answer questions such as "is the pain coming from the tooth or another structure?", and "is the tooth alive or dead". These are very important questions in a wide variety of individuals presenting with acute and chronic orofacial pain. In the present study we will measure pulpal blood flow using pulse oximeter in patients who are already undergoing extractions. We will then look to see whether these clinically measured physiologic indicators of tooth vitality are similar to the histological presentation of the extracted teeth.

1.2 **Rationale**

The purpose of this study is to assess tooth health by using a pulse oximeter which measures the blood flow within the tooth. We hypothesize that if we can measure both sensation and blood flow in a tooth, we will be able to better determine if the tooth is "alive or dead". In the future, this method may help determine which teeth are diseased and require dental treatments. The objective of the study is to measure sensation as well as blood flow in a tooth, for potential use in dentistry.

Our specific aims are:

Aim - 1: To measure pulpal blood flow using pulse oximeter and laser Doppler Flowmeter (LDF)

Aim - 2: To measure tooth vitality using Cold, Electrical Pulp tester (EPT), percussion and palpation testing

Aim - 3: To assess histological presentation of the pulp the extracted teeth

Aim - 4: To evaluate the relationships between the Aims 1-3 to determine if pulpal blood flow is a reliable indicator of tooth vitality.

1.3 **Potential Risks and Benefits**

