1.3.2 Potential Benefits

Participants are not expected to receive any personal benefits from being in this study.

OBJECTIVES

1.4 **Study Objectives**

The purpose of this study is to assess tooth health by using a pulse oximeter which measures the blood flow within the tooth. We hypothesize that if we can measure both sensation and blood flow in a tooth, we will be able to better determine if the tooth is "alive or dead". In the future, this method may help determine which teeth are diseased and require dental treatments.

Our specific aims are:

Aim - 1: To measure pulpal blood flow using pulse oximeter and Laser Doppler Flowmeter

Aim - 2: To measure tooth vitality using Cold, Electrical Pulp tester (EPT) , percussion and palpation testing

Aim - 3: To assess histological presentation of the pulp the extracted teeth

Aim - 4: To evaluate the relationships between the Aims 1-3 to determine if pulpal blood flow is a reliable indicator of tooth vitality.

1.5 **Study Outcome Measures**

Primary Outcomes Measures: Correlation Between Subjective and Objective Measurements of Pulpal Status

- Subjective Measurements Pulpal Status: Conventional pulpal diagnosis using cold test [Endo Ice, Coltene/Whaledent, Cuyahoga Falls, OH, USA] and Electrical Pulp Test -EPT S[Kerr Vitality Scanner, SybronEndo] testing and recorded, along with vertical and lateral percussion and palpation responses. Conventional pulpal diagnosis assessment would be used for teeth that are planned for extraction and additional teeth (10 total) in each participant
- *Objective Measurements Pulpal Status:* Measurements obtained from pulse oximeter gives a series of reading of oxygen saturation level, and pulse. Pulse oximeter measurements would be used for teeth that are planned for extraction and also up to 2-5 additional teeth in each participant

Exploratory Outcomes:

- *Systemic Vital Sign Measurements:* Blood pressure and pulse recording will be obtained from the recorded values from the participant's chart.
- *Histological Assessment of the Extracted Teeth:* Upon completion of extraction, the teeth will be placed in formalin-containing bottle. After formalin fixation, the teeth will be prepared for histological examination using 10% EDTA for demineralization. Following that, the teeth are trimmed, embedded in paraplast and cut longitudinally to obtain 6um thick section. The sections were stained with H&E and examined with a light microscope.

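### The laser Doppler reading is always taken after cold, EPT and percussion testing, so the exploratory LDF results for Aims 1 and 4 cannot be separated from any carry-over of those tests

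*Combined protocol and SAP*

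**What the plan says.** The sequence is given twice, in the Schematic of Study Design (Protocol Summary) and under Study-Related Procedure (Study Design). The two agree on order:

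1. Palpation: "The researcher initially will palpate the gum around selected teeth and record any discomfort".
2. The oximeter clip is fitted "to measure blood flow by measuring the presence of pulse in these teeth for approximately for 15-30 seconds".
3. The oximeter stays on: "The clip will remain on the tooth for additional 2-3 minutes to continually measuring pulse while the following tests are taken place". The cold pellet is "placed on the surface of that tooth for approximately 15 seconds or till participant reports any sensation of cold". The EPT probe "will be placed on the surface of that tooth for approximately 15 seconds or till participant reports any tingling sensation". Percussion follows, with no stated duration. Each of the three tests is followed by a 30-second wait.
4. The clip comes off, the sensor is exchanged, and LDF is read for about 15-30 seconds: "The plastic clip will be placed back over the teeth previously tested to measure the blood flow with the LDF".

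Neither description mentions an LDF reading before the tests, a varied device order, or a check that flow has returned to baseline.

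Aim 1 (sections 1.2 and 1.4) names both devices. Aim 4 is "To evaluate the relationships between the Aims 1-3 to determine if pulpal blood flow is a reliable indicator of tooth vitality". Section 1.5 builds the primary outcome on the oximeter and the conventional tests, and lists LDF and histology as exploratory. The Final Analysis Plan (1.22) names no LDF analysis. Form 2 has one row for the oximeter and one for LDF per tooth, with no field for the time of a reading.

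**The concern.** LDF is one of the two blood-flow measures in Aim 1, and Aim 4 uses blood flow to judge vitality. If cold, electrical or mechanical stimulation leaves pulpal flow altered for a minute or two, the LDF value mixes resting flow with the response to testing. There is no LDF value from before the tests to show this.

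Two things would be at stake. First, a difference between LDF and oximeter results could come from the device or from the moment of reading. Second, the stimulation that precedes LDF depends on whether the tooth responded to cold and EPT. Those are Aim 2 measures, to which Aim 4 relates the LDF value. A carry-over effect could therefore differ between responding and non-responding teeth, which would affect how well LDF separates them as well as its average level.

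**Working it through.** **Inputs.** From Study-Related Procedure: cold contact c = 0 to 15 s, EPT contact e = 0 to 15 s (reading the rule as stopping at whichever comes first), and a wait of 30 s after each test. Percussion time p is not given; I assume 0 to 60 s. Sensor-swap time is also not given, so every gap below excludes it.

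**Check against the plan's own figure.** Length of the test block = c + 30 + e + 30 + p + 30 = 90 + c + e + p.
- With c = e = 15: 120 + p, which is 120 to 180 s. This agrees with the stated 2-3 minutes.
- With an immediate response to both tests (c = e = 0): 90 + p.

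**Gap between each test and LDF.**
- From the end of percussion: 30 s.
- From the end of EPT: 30 + p + 30 = 60 + p, or 60 to 120 s.
- From the end of cold: 30 + e + 30 + p + 30 = 90 + e + p, or 90 to 165 s.

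**Dependence on response.** Contact time before LDF is c + e.
- It is near 0 s for a tooth that responds at once to both tests, and 30 s for one that responds to neither.
- The gap after cold is 90 + p with an immediate EPT response and 105 + p with none. Both the dose of stimulation and the delay therefore depend on the test results.

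**When each device is read.**

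| | Before the tests | During | After |
|---|---|---|---|
| Oximeter | 15-30 s | 2-3 min | none |
| LDF | none | none | 15-30 s |

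The devices share no period, so no analysis can separate device from period. Most of the oximeter record is also not at rest: the share taken during the tests runs from 120/(30 + 120) = 80% to 180/(15 + 180) = 92%. The documents do not say which part is the analysed value.

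**Uncertain delay.** The text does not say whether LDF follows each tooth or comes after all teeth are tested. For illustration, take four teeth, the number of blocks on Form 2. If LDF follows all of them, the first tooth waits a further 3 x (15 + 120) = 405 s to 3 x (30 + 180) = 630 s, about 6.8 to 10.5 minutes. With no recorded times, this cannot be reconstructed.

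**The case against.** The case for leaving the order alone has real substance.

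- **The primary outcome is untouched.** It uses the oximeter with the conventional tests. LDF is exploratory, the Final Analysis Plan does not name it, and sections 1.12 and 1.31 omit it. This stands and limits severity.
- **No device comparison is planned.** A reader might infer from Aim 1 that the devices are to be compared. The aim only says to measure with each, and they record different quantities (saturation and pulse against blood velocity). This stands. Aim 4 nevertheless relates Aim 1 as a whole to Aims 2 and 3, so LDF has a role there.
- **The oximeter is not purely a resting measure.** A reader might infer that it is read at rest and that all carry-over falls on LDF. It also records throughout the tests, and palpation precedes both devices. What remains is narrower: the oximeter has a window before the three tests, and LDF has none.
- **The waits may be long enough.** They may, but the documents neither justify them nor provide a check.
- **The reading may be robust.** The procedure describes detecting the presence of a pulse, and a modest shift in flow need not change a yes/no result. Section 1.5, however, describes LDF as a series of velocity readings, which would be open to a shift.
- **Reading the primary device first is defensible.** That is true, and it is a cost of the reordering proposed here.

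**Conclusion.** The concern holds in a limited form. LDF is always a post-stimulus reading, and the stimulation before it varies with the cold and EPT results. The consequence falls on the exploratory LDF results used in Aims 1 and 4, and on any LDF-oximeter or LDF-histology comparison. Severity is minor to moderate.

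The order and the minimum gaps (30, 60 and 90 s) come from the procedure text. The longer gaps rest on the assumed percussion time, and the dependence on response rests on reading the 15-second rule as whichever comes first.

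A reader might go further and infer that discrimination by LDF is biased by a definite amount, or that keeping the oximeter on shows the investigators expect flow to change. The documents support neither. They give no carry-over size, direction or duration, and no reason for the continuous recording. The point is that the plan could not detect or remove a carry-over effect if one exists.

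**What to change.** Reorder the measurements. After palpation, take the 15-30 s LDF reading on the selected teeth, swap to the oximeter, take its 15-30 s pre-test reading, then run cold, EPT and percussion with the oximeter clip on as now described. Also:

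- add a time field to Form 2 for each reading;
- name the pre-test LDF and pre-test oximeter windows as the values used in Aim 4.

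The cost is a change of procedure wording and a small form change; the readings and the number of sensor swaps stay the same. Section 1.3.1 says that clinical decisions will not rest on either device. The downside is that the oximeter reading then follows an earlier clip placement and the device order is still fixed. Alternating across participants which device is read first, with both before the tests, would address that.

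If the present order is kept, state that LDF is a post-stimulus reading, say whether it follows each tooth or all teeth, and state that the two devices will not be compared.
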